VSI, Visceral Sensitivity Index
IBS-QOL, IBS-quality of life
TpH-1, Tryptophan hydroxylase-1
SNPs, Single nucleotide polymorphisms
OTU, operational taxonomic units
LEfSE, linear discriminant analysis effect size
AMOVA, analysis of molecular variance
eCRF, electronic Case Report Form
PHI, Protected Health Information
GCP, Good Clinical Practice
AE, Adverse Event

1 BACKGROUND/SCIENTIFIC RATIONALE

Irritable bowel syndrome (IBS) is a common but incompletely understood condition that leads to significant morbidity and substantial health care expenditures (1,2). IBS is likely a multifactorial disorder including disordered motility, immune activation, gut barrier dysfunction, visceral hypersensitivity, and altered brain-gut interactions (3–5).

The role of the gut microbiota is increasingly being recognized for its potential role *in the pathogenesis of IBS*. Humans are host to a diverse community of microbes collectively known as the human microbiota, of which the vast majority live in the gut (6). The gut microbiota normally interacts closely with the intestinal epithelial cells as well as the enteric immune and nervous system, which comprises the microbiota-gut-brain axis (7). There is a symbiotic relationship between the microbiota and host with the gut microbiome providing essential functions, including maintenance of the gut epithelial barrier and immune function (8). However, alterations in the structure and community function of the fecal microbiota may have a significant role in the pathogenesis of human disease, including IBS. Acute gastroenteritis leads to an increased risk for development of post-infectious IBS and is associated with altered gut microbiota, increased permeability and immune activation (9–11). Further evidence of the role of gut microbiota in IBS is shown by experiments where transfer of microbiota from patients with IBS to germ-free mice leads to rapid GI transit, impaired gut barrier function, and visceral hypersensitivity (12,13).

Several studies have reported an increase in the relative abundance of Firmicutes, a reduction in the relative abundance of Bacteroidetes, and decrease in microbial diversity (14–16). However, studies are often conflicting and a specific microbial signature has not been discovered to date in IBS (17–19). Incomplete phenotypic characterization, small sample sizes, the cross-sectional nature of study design, and probable heterogeneity of the patient populations also limited prior studies. In addition, previous studies have not taken differences in diet or stool consistency into consideration despite the fact that these factors heavily influence the composition of the gut microbiota (20,21).

Small intestinal bacterial overgrowth (SIBO) has also been postulated to be an *important pathophysiologic factor* in the pathogenesis of IBS (22–24). SIBO is defined as presence of bacteria in excess of 10^5 colony-forming units per milliliter on culture of small bowel aspirates [34]. Prevalence figures of SIBO in IBS range from 4–64% depending on the method of testing (26). SIBO is characterized by symptoms of diarrhea, abdominal pain, bloating, and gas. It has been proposed that SIBO may lead to immune activation, triggering low-grade inflammation, epithelial barrier dysfunction, and visceral hyperalgesia seen in IBS (27). Meanwhile, antibiotics improve symptoms in IBS patients with SIBO while those patients who achieved bacterial eradication showed the greatest symptomatic response (23). However, little is known about the specifics of the gut microbiota in SIBO and whether these conditions are separate or overlapping entities.

Small bowel aspirate and culture is an accepted means of quantifying upper intestinal bacteria, but this approach is time consuming, invasive, and has a high false-negative rate (28). As a consequence, hydrogen breath tests have largely supplanted intestinal cultures as measures of SIBO. There is some controversy regarding the substrate that is utilized in hydrogen breath

tests. Lactulose has been advocated as a preferred substrate as it is not absorbed in the GI tract. However, simultaneous testing using scintigraphy and lactulose hydrogen breath testing (LGBT) demonstrated that abnormal findings with LGBT represent rapid orocecal transit rather than SIBO (29). Glucose is another substrate that is commonly employed in hydrogen breath testing. Although glucose is primarily absorbed in the proximal small bowel and therefore may miss distal SIBO, this is still the most common and widely available non-invasive test to diagnose SIBO (30).

Despite our advances in understanding the pathophysiology of IBS, there are still **unmet needs** in terms of treatment options. Rifaximin is a non-absorbable antibiotic that has been shown to improve symptoms in the diarrhea-predominant subtype of IBS (IBS-D) (31,32). However, mechanisms by which rifaximin leads to improvement in IBS-D are still unknown. In vitro studies suggest that rifaximin may prevent changes in barrier dysfunction and reverse mucosal inflammation by modulating bacteria in the small intestine (33). Conversely, prior studies have not demonstrated significant effects of rifaximin on fecal microbial composition (34,35). This is likely because rifaximin is insoluble in the colon and has antimicrobial effects primarily in the small bowel (36). Furthermore, rifaximin leads to improvement in symptoms in *only 40% of IBS patients* with a therapeutic gain of 9% over placebo. Because of these observations, one could argue that rifaximin may be effective only in those IBS patients who have concomitant SIBO. Indeed, a recent study demonstrated that those IBS patients with SIBO had a significantly increased response to rifaximin compared with those IBS patients without SIBO (37).

Dietary modification has also been advocated as a potential treatment option in IBS-D. The vast majority of IBS patients believe certain foods trigger their IBS symptoms (38). Fermentable oligosaccharides, disaccharides, monosaccharides, and polyols (FODMAP) are short-chain, poorly absorbable carbohydrates. Recently, a diet low in FODMAP has been shown to improve symptoms in up to 76% of IBS patients (39,40). However, two recent randomized controlled trials failed to show a low FODMAP diet was superior to traditional IBS dietary advice in controlling symptoms (41,42). Furthermore, improvement in symptoms was reported by *only 50% of patients on low FODMAP diets*. Moreover, the exact mechanism by which a low FODMAP diet improves symptoms in IBS is still unknown. It is postulated that the gut microbiota are critical in generation of symptoms in the presence of dietary FODMAPs and lead to production of gases, including hydrogen, CO₂, and methane. This may generate symptoms in IBS particularly in the setting of visceral hypersensitivity (43).

Identifying those subjects who are *most likely to respond* to a low FODMAP diet is clearly needed but has been a vexing problem. Hydrogen breath testing has been advocated as a potential tool to identify subjects that malabsorb FODMAPs (e.g. lactose, fructose, sorbitol, and mannitol) and thereby might have better response to dietary FODMAP restriction. However, questions regarding the reproducibility of breath testing as well as standardization of the test in this setting are still unanswered (44). Furthermore, it was recently shown that a lactulose breath test could not discriminate between responders and non-responders to low FODMAP diets (45). Interestingly, a recent study in pediatric IBS subjects demonstrated that responders to a low FODMAP diet had *different fecal microbial composition* at baseline compared with non-responders (46). As the gut microbiota is postulated to be one of the main mediators in the pathogenesis of symptoms in IBS and FODMAP intake, this suggests that alterations in the fecal microbiota may predict response to dietary restriction of FODMAP. Genetic variability in

tryptophan hydroxylase-1 (TpH-1) and sucrase-isomaltase single nucleotide polymorphisms (SNPs) have been demonstrated in IBS patients (47,48). Unpublished data suggest that differences in TpH-1 SNPs may also potentially identify responders vs. non-responders to treatments, such as low FODMAP diet, in IBS. Finally, a recent study suggested that treatment with low FODMAP diet may lead to improvement in cytokine profiles (49).

Taken collectively, our current therapeutic options are quite limited in IBS-D and improve symptoms in only $\leq 50\%$ of subjects in the best-case scenarios, which we believe is a consequence of multiple pathogenic factors. Given that IBS is a heterogeneous condition, there is a **pressing need to stratify IBS patients into distinct subtypes** to optimize responses to diverse therapies including antibiotics versus dietary measures. In the investigations included in this proposal, we will test the hypotheses that: (i) distinct IBS-D phenotypes with characteristic clinical features can be generated by identifying the presence or absence of SIBO and by defining fecal microbial populations, and (ii) longitudinal analyses using microbiota-derived metrics as well as SIBO status may provide important details into how these treatments improve symptoms in IBS and may also provide clues on which patients may respond to different therapies.

2 OBJECTIVES

Aim 1: Randomize IBS-D subjects to receive either treatment with a nonabsorbable antibiotic rifaximin vs. low FODMAP dietary intervention.

- a) 200 IBS-D patients will be carefully phenotyped using validated questionnaires (IBS symptoms, stool form, psychological function, quality of life) and diet analysis.
- b) IBS-D subjects will undergo baseline testing including glucose hydrogen breath tests (GHBT) to define the presence of SIBO. Fecal microbiota will also be characterized by α - and β -diversity and dominant phyla on 16S RNA analyses.
- c) IBS-D subjects will be randomized to receive either rifaximin 550 mg three times daily $\times 14$ days or low FODMAP diet $\times 4$ weeks under direction of study bionutritionist.
- d) The primary outcome will be changes in mean daily pain or bloating by visual analog scale (VAS) after intervention compared with baseline. Responders to intervention will be defined by $\geq 30\%$ reductions in mean daily pain or bloating by VAS compared with baseline. Secondary outcomes will be defined by reduction in IBS Symptom Severity Scale by ≥ 50 compared with baseline.
- e) Other secondary outcomes, including GI symptoms, stool form, psychological function, quality of life, and diet intake, will be compared to determine if subjects present differently.

Aim 2: Determine using longitudinal analyses how SIBO status and fecal microbiota features associate with response to treatment with rifaximin or a low FODMAP dietary intervention.

- a) Fecal microbial analyses will be repeated at 2, 4 and 5 weeks while GHBT will be repeated at the end of the intervention.

- b) The primary aim will be change in fecal microbial diversity after intervention compared with baseline. We hypothesize that low FODMAP diet will result in a 10-15% increase in diversity in fecal microbiota compared with baseline.
- c) Secondary outcomes including response to treatment with rifaximin or low FODMAP diet will be related to the (i) presence of SIBO on initial testing, (ii) persistence of SIBO after intervention, (iii) abnormal α - and β -diversity on initial testing, (iv) changes in α - and β -diversity as well as in dominant microbial phyla at 2, 4 and 5 weeks, and (v) changes in serum cytokine profiles, including TNF- α , IL-1 β , IL-6, IL-8, and IL-10.
- d) Other outcomes that will be assessed include differences in tryptophan hydroxylase-1 (TpH-1) and sucrase-isomaltase single nucleotide polymorphisms (SNPs) in different cohorts of IBS-D patients.

Aim 3: Develop a predictive model to identify subsets of IBS-D patients responsive to treatment.

- a) We will develop and validate a predictive model of response to low FODMAP diet using data from the subjects randomized to a low FODMAP diet (Aim 1) combined with existing data from a separate cohort of IBS-D subjects previously treated with a low FODMAP diet (HUM 00053274).

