6 STUDY DESIGN AND PROCEDURES

Specific Aim 1: Randomize IBS-D subjects to receive either a nonabsorbable antibiotic rifaximin vs. low FODMAP dietary intervention.

1A. Research Approach:

200 IBS-D subjects will be carefully phenotyped using validated questionnaires (IBS symptoms, stool form, psychological function, quality of life) and diet analysis. IBS-D subjects will also undergo baseline testing including GHBT as well as fecal microbial analysis. IBS-D subjects will then be randomized to receive either rifaximin or low FODMAP diet intervention at the initial screening visit. Efficacy of therapies will be monitored with validated questionnaires to track symptomatic improvement. The primary outcome will be changes in mean daily pain or bloating after intervention compared with baseline. Responders to intervention will be defined as $\geq 30\%$ reduction in mean daily pain or bloating by visual analog scale (VAS) compared with baseline. Secondary outcomes will monitor changes in IBS-Symptom Severity Score as well as differences in GI symptoms, stool form, psychological function, quality of life, and dietary intake before and after intervention.

1B. Experimental Methods:

Subject Recruitment: 200 adult subjects ≥ 18 years of age who meet Rome IV criteria for IBS-D will be enrolled in the study. Women of childbearing age will undergo a urine pregnancy test to exclude the possibility of pregnancy. Women who are breastfeeding will also be excluded. IBS-D subjects will be excluded if they have underlying celiac disease, inflammatory bowel disease, or other organic disease that could explain their symptoms. All IBS-D subjects will have prior sigmoidoscopy or colonoscopy with mucosal biopsies within the past 2 years to rule out microscopic colitis. IBS-D subjects with a history of GI tract surgery, except for appendectomy, will also be excluded from the study. Antibiotics taken within 3 months prior to enrollment will not be permitted (54). IBS-D subjects on probiotics must discontinue their use at least 1 month prior to fecal collection. IBS medications, including anti-depressants, will be allowed if the dose has been stable for at least 1 month before inclusion. Medications will be carefully tracked to follow any potential confounding issues. IBS-D subjects who have previously received formal

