Trial Protocol: In order to minimize unequal allocation between arms, IBS-D subjects will be randomized using block randomization with random permuted sizes of 2 or 4 in a 1:1 ratio into two arms: one group will undergo treatment with rifaximin 550 mg three times daily for 14 days. The second group will be placed on a low FODMAP diet (≤ 9 grams per day as previously described) for 4 weeks (40,64,65). IBS-D subjects undergoing dietary intervention will undergo consultation with a bionutritionist knowledgeable in low FODMAP diets. A diet plan will be implemented and individualized to subjects based on information from their dietary history. Written information regarding allowable vs. non-allowable food items will be provided to IBS-D subjects and bionutritionists will be available during the study for further education. IBS-D subjects randomized to the low FODMAP diet group will meet with the GI nutritionist at the completion of the 2nd week of dietary intervention to answer any potential questions regarding the diet. IBS-D subjects will complete a 24-hour dietary recall each week or every two weeks during the 4-week dietary intervention to ensure compliance.

Symptom Assessment: IBS-D subjects will record stool frequency, BSFS, and symptom scores for abdominal pain and bloating daily on a diary card. IBS-D subjects will complete questionnaires on a weekly basis during study visits to determine changes in symptoms. Responders to intervention arm (both rifaximin and low FODMAP diet) will be defined as $\geq 30\%$ reductions in mean daily pain or bloating compared with baseline. Secondary outcomes, including reduction in IBS Symptom Severity Scale by ≥ 50 compared with baseline at the end of the interventional arm, will also be monitored. These are both considered to reflect clinically meaningful improvements in IBS (55,57). IBS-D subjects will be seen on a weekly or biweekly basis and diary cards will be collected. Adherence to medications or dietary intervention will also be assessed at that time.

Specific Aim 2: Determine using longitudinal analyses how SIBO status and fecal microbiota-derived metrics associate with response to treatment with rifaximin or a low FODMAP dietary intervention.

2A. Research Approach:

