8 DATA ANALYSIS

Procedure for Accounting for Missing, Unused, and Spurious Data: The primary outcome measure in our study is changes in mean daily pain or bloating after intervention with rifaximin or low FODMAP diet compared with baseline. We will use multiple imputation with 10 imputed datasets to replace missing values on outcome and predictor variables [77]. If 10 imputed datasets are not sufficient to ensure stability of estimates, we will use 20 imputed datasets. This allows for maximal use of available data while maximizing statistical power.

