10 STATISTICAL CONSIDERATIONS

Aim 1:

All of the interventional analyses will be analyzed on an intention-to-treat basis. Each IBS-D subject will act as his/her own control for analysis of the effects of either rifaximin or low FODMAP diet intervention. This paired design inherently eliminates a significant amount of bias/confounding and affords increased statistical power. We will power our study to detect a $\geq 30\%$ improvement in mean daily bloating or abdominal pain after intervention compared with baseline. Using available data from a US study on low FODMAP diet in IBS patients (42), we conservatively estimate that we will require 14 IBS-D subjects in each arm to have $>90\%$ power to detect a mean difference of 1.7 in abdominal bloating scores after intervention via paired t-tests with the expected standard deviation (SD) of ± 1.8 . Thus, our expected enrollment of 32 IBS-D subjects in each arm will be more than sufficient for analyzing this aim (see biostatistical analysis for Aim 2), even if the SD is nearly two-fold larger than expected.

Aim 2:

We will examine both inter- and intra-individual variability in microbiota-derived metrics. We plan to use a paired design to eliminate a significant amount of bias/confounding and increase statistical power. We anticipate that there will be some variability in the three samples collected prior to treatment, and various techniques will be employed to average these data so they are incorporated as the baseline. For example, for α diversity (Shannon index) a simple average of the three time points will be sufficient to

establish a baseline α diversity. Similar techniques will be applied to other community structure metrics, to create “deltas” between post-treatment time points and the baseline.

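### The Aim 1 primary outcome is change in pain or bloating with no rule for which decides, so each arm has two unadjusted chances of a positive result, and only bloating was sized

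*Combined protocol and SAP*

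**What the plan says.** The either-or appears wherever the primary outcome is defined.

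- Section 2, Aim 1(d): "The primary outcome will be changes in mean daily pain or bloating by visual analog scale (VAS".
- Section 6, 1A: "The primary outcome will be changes in mean daily pain or bloating after intervention compared with baseline".
- Section 8: "The primary outcome measure in our study is changes in mean daily pain or bloating after intervention with rifaximin or low FODMAP diet".

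The responder definition has the same form: a fall of at least 30%, described in Section 2 as "reductions in mean daily pain or bloating by VAS compared with baseline". Section 6, 1B applies it to both arms: "Responders to intervention arm (both rifaximin and low FODMAP diet) will be defined as" such "reductions in mean daily pain or bloating compared with baseline".

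Section 10 analyses each arm before against after: "Each IBS-D subject will act as his/her own control for analysis of the effects of either rifaximin or low FODMAP diet intervention". Its general power sentence names both symptoms, but the one calculation is "to detect a mean difference of 1.7 in abdominal bloating scores after intervention via paired t-tests", with an SD of 1.8, giving 14 per arm for more than 90% power against an expected 32. No effect size or SD for pain is given.

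No section says whether the two symptoms form one composite, two co-primary outcomes, an ordered pair, or a choice. No alpha is stated. The only false-discovery provision is LEfSe for the taxa in Aim 2.

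**The concern.** An outcome worded as one symptom or the other, with a paired t-test for each and no rule linking them, lets an arm be reported as positive on either. The nominal error rate then applies to each test but not to the primary claim. It also leaves room to settle on the primary symptom after the data are seen.

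The responder rule raises a different question. There the two chances belong to the patient. Daily symptom means fluctuate, so some patients will cross a 30% threshold with no real change, and more will do so when either of two scores may cross it. Response is what Aim 2(c) relates to SIBO, diversity and cytokines, and it is the grouping in the Section 10 β-diversity power statement. Misclassified patients blur those contrasts, and a larger sample does not correct the labels.

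**Working it through.** **1. The plan's own figure.** Inputs from Section 10: change 1.7, SD 1.8 (taken as the SD of the paired difference; the section does not say which SD it is), n = 14. Two-sided alpha 0.05 is assumed because none is stated. Power comes from the noncentral t with n − 1 degrees of freedom and noncentrality (1.7/1.8)√n.

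- n = 13: power 0.878
- n = 14: power 0.904

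The minimum is 14, which matches the plan. The bloating calculation is correct.

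**2. False-positive chance for the change outcome, per arm.** Suppose neither symptom changes and each is tested at two-sided 0.05. The chance of at least one significant result is 1 − P(|Z₁| ≤ 1.96 and |Z₂| ≤ 1.96), where Z₁ and Z₂ are bivariate normal with correlation r between the two changes. The documents do not give r, so a range is shown.

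| r | chance of at least one false positive |
|---|---|
| 0 | 1 − 0.95² = 9.75% |
| 0.5 | 9.1% |
| 0.7 | 8.4% |
| 0.8 | 7.8% |
| 0.9 | 7.0% |

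**3. What control would cost in sample size.** Splitting alpha gives 0.05/2 = 0.025 per symptom. With 1.7 and 1.8:

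- power at n = 14 falls from 0.904 to 0.827
- the minimum n for 90% power rises from 14 to 17
- power at n = 32 is 0.998

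For pain, no input exists. If its SD were also 1.8, power at n = 32 and alpha 0.025 would be:

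| true pain change | power |
|---|---|
| 0.8 | 57% |
| 1.0 | 78% |
| 1.2 | 92% |
| 1.5 | 99% |
| 1.7 | 99.8% |

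**4. Chance responders under the 30% rule.** None of these inputs is in the documents as used here; all are assumptions. Patients' usual levels average 5.0 for pain and 5.5 for bloating, with SD 1.8 and correlation 0.6. Baseline and follow-up means each add noise with correlation 0.5 between symptoms. Entry requires the average of the two baselines to be at least 4. There is no true change. The noise SD of a weekly mean is varied because the result depends on it.

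| noise SD | either symptom | bloating alone |
|---|---|---|
| 0.5 | about 2% | about 1% |
| 0.75 | about 9% | about 5% |
| 1.0 | about 18% | about 10% |
| 1.25 | about 26% | about 15% |

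The absolute rates vary more than tenfold, but the ratio stays near two (for example 18/10 = 1.8 and 26/15 = 1.7).

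**The case against.** The best reply is that the plan states neither a success criterion nor an alpha, so it does not actually declare an arm positive on either symptom. That is fair, and the figures in step 2 are conditional on testing both at 0.05. A single prespecified composite would carry no such inflation. But no composite is defined, the planned test is a paired t-test, and nothing stops both being run.

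A second reply is that the sample is ample. This stands: 17 is well below 32 per arm, and further below the 100 per arm implied by the 200 subjects in Sections 2, 4 and 6. It makes the fix cheap but does not remove the need for it.

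Third, the responder rule is one binary composite, and Section 6 gives a reason for its 30% threshold. This also stands. The rule changes what is measured without inflating type I error.

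Stronger readings that a reader might infer, and that the documents do not support:

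- **One error rate pooled over both arms.** Section 10 treats the effect of each intervention as its own question, so the per-arm figure is the defensible one.
- **Response on a symptom that was trivial at baseline.** This depends on how the Section 4 entry rule is read: an average of 4 or more could apply to each symptom or to the two together. Under the assumptions of step 4 (noise SD 1.0), the either-or rate is about 18% on either reading, so a minimum baseline would do little.
- **The trial is underpowered for pain.** Power for pain is unknown, not shown to be low.
- **The Aim 3 model learns this label.** Sections 2 and 6 speak only of response to the diet, pooled with an outside cohort whose response measure is not described.

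**Conclusion.** The point holds as a fault in endpoint definition and error control. The primary outcome leaves two symptoms open with no rule between them. If both are tested at an assumed two-sided 0.05, the per-arm false-positive chance is about 7% to 10%, depending on a correlation the documents do not give. The sizing covers bloating only and is arithmetically right. The consequence for sample size is small, provided that the pain effect and SD are like those for bloating.

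The responder rule is a lesser and separate matter: about twice as many chance responders as on bloating alone, under assumed noise levels, and a label that does not show which symptom improved. This bears on the Aim 2 response associations, and on Aim 3 only if the same definition serves as its outcome.

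**What to change.** In Sections 2, 6, 8 and 10, name change in mean daily bloating, the measure already sized, as the single Aim 1 primary outcome in each arm. Test pain next, at the same alpha, only if bloating succeeds. If the two symptoms must rank equally, use Holm across them within each arm. In either case state alpha and sidedness, and give an expected effect and SD for pain.

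Define the 30% responder on the same primary score and report the either-or rate as secondary. State which response definition Aim 2 uses, and whether Aim 3 uses it as well.

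This needs wording only, with no new data. Testing in sequence leaves the bloating requirement at 14 per arm; splitting alpha takes it to 17. There are two downsides: the response rate will be lower, and under the ordered scheme a benefit confined to pain could not be claimed as confirmed.
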